10.1 Restrictions during the study

The following restrictions apply while the patient is receiving study treatment and for the specified times before and after:

Female patient of child-bearing potential:

• Female patients of childbearing potential who are not abstinent and intend to be sexually active with a non-sterilized male partner must use at least 1 highly effective method of contraception (Table 1) from the time of screening throughout the total duration of the drug treatment and the drug washout period (90 days after the last dose of durvalumab monotherapy). Non-sterilized male partners of a female patient of childbearing potential must use male condom plus spermicide throughout this period. Cessation of birth control after this point should be discussed with a responsible physician. Periodic abstinence, the rhythm method, and the withdrawal method are not acceptable methods of birth control. Female patients should also refrain from breastfeeding throughout this period.

Male patients with a female partner of childbearing potential:

- Non-sterilized male patients who are not abstinent and intend to be sexually active with a female
 partner of childbearing potential must use a male condom plus spermicide from the time of screening
 throughout the total duration of the drug treatment and the drug washout period (90 days after the
 last dose of durvalumab monotherapy). Periodic abstinence, the rhythm method, and the withdrawal
 method are not acceptable methods of contraception. Male patients should refrain from sperm
 donation throughout this period.
- Female partners (of childbearing potential) of male patients must also use a highly effective method of contraception throughout this period (Table 1).

N.B Females of childbearing potential are defined as those who are not surgically sterile (i.e. bilateral salpingectomy, bilateral oophorectomy, or complete hysterectomy) or post-menopausal.

Women will be considered post-menopausal if they have been amenorrheic for 12 months without an alternative medical cause. The following age-specific requirements apply:

 Women <50 years of age would be considered post-menopausal if they have been amenorrheic for 12 months or more following cessation of exogenous hormonal treatments and if they have luteinizing

hormone and follicle-stimulating hormone levels in the post-menopausal range for the institution.

Women ≥50 years of age would be considered post-menopausal if they have been amenorrheic for 12 months or more following cessation of all exogenous hormonal treatments, had radiation-induced menopause with last menses >1 year ago, had chemotherapy-induced menopause with last menses >1 year ago.

Highly effective methods of contraception, defined as one that results in a low failure rate (i.e. less than 1% per year) when used consistently and correctly are described in Table 1. Note that some contraception methods are not considered highly effective (e.g. male or female condom with or without spermicide; female cap, diaphragm, or sponge with or without spermicide; non-copper containing intrauterine device; progestogen-only oral hormonal contraceptive pills where inhibition of ovulation is not the primary mode of action [excluding Cerazette/desogestrel which is considered highly effective]; and triphasic combined oral contraceptive pills).

Table 1 Highly Effective Methods of Contraception (<1% Failure Rate)

Tuble 1	e 1 Highly Effective inethous of Contraception (<1% Fahilire Rate)				
•	Barrier/Intrauterine methods	Hormonal Methods			
•	Copper T intrauterine device Levonorgestrel-releasing intrauterine system (e.g., Mirena®) ^a	 Implants: Etonogestrel-releasing implants: e.g. Implanon® or Norplant® Intravaginal: Ethinylestradiol/etonogestrel-releasing intravaginal devices: e.g. NuvaRing® Injection: Medroxyprogesterone injection: e.g. Depo- Provera® Combined Pill: Normal and low dose combined oral contraceptive pill Patch: Norelgestromin/ethinylestradiol-releasing transdermal system: e.g. Ortho Evra® Minipill: Progesterone based oral contraceptive pill using desogestrel: Cerazette® is currently the only highly effective progesterone-based 			

This is also considered a hormonal method

10.1.1 Blood donation

Patients should not donate blood while participating in this study, or for at least 90 days following the last infusion of durvalumab or 90 days after receipt of the final dose of durvalumab.

10.2 Concomitant treatment(s)

10.2.1 Permitted concomitant medications

Table 2 Supportive Medications

Supportive medication/class of drug:	Usage:
Concomitant medications or treatments (e.g., acetaminophen or	To be administered as
diphenhydramine) deemed necessary to provide adequate prophylactic	prescribed by the Investigator
or supportive care, except for those medications identified as	
"prohibited," as listed above	
Best supportive care (including antibiotics, nutritional support,	Should be used, when
correction of metabolic disorders, optimal symptom control, and pain	necessary, for all patients
management [including palliative RT to non-target lesions])	
Inactivated viruses, such as those in the influenza vaccine	Permitted

10.2.2 Excluded concomitant medications

Table 3 Prohibited Concomitant Medications

Prohibited medication/class of drug:	Usage:		
Any investigational anticancer therapy other than	Should not be given concomitantly whilst the		
those under investigation in this study	patient is on study treatment		
mAbs against CTLA-4, PD-1, or PD-L1 other than	Should not be given concomitantly whilst the		
those under investigation in this study	patient is on study treatment		
Any concurrent chemotherapy, immunotherapy, or biologic or hormonal therapy for cancer treatment other than those under investigation in this study Immunosuppressive medications including, but not limited to, systemic corticosteroids at doses exceeding 10 mg/day of prednisone or equivalent, methotrexate, azathioprine, and tumor necrosis factor-α blockers	Should not be given concomitantly whilst the patient is on study treatment. (Concurrent use of hormones for non-cancer-related conditions [e.g., insulin for diabetes and hormone replacement therapy] is acceptable. Local treatment of isolated lesions, excluding target lesions, for palliative intent is acceptable [e.g., by local surgery or RT]) Should not be given concomitantly or used for premedication prior to the I-O infusions. The following are allowed exceptions: Use of immunosuppressive medications for the management of IP-related AEs Short-term antiemetic therapy in relation with chemotherapy-courses For the treatment of hypersensitivity reactions caused by the study treatment Use in patients with contrast allergy Use of inhaled, topical and intranasal corticosteroids is permitted A temporary period of steroids will be allowed if		
	clinically indicated and considered to be essential		
	for the management of non-immunotherapy		
	related events experienced by the patient (e.g.,		
	chronic obstructive pulmonary disease, radiation, nausea, etc.).		
Live attenuated vaccines	Should not be given through 30 days after the last dose of IP (including SoC)		
Herbal and natural remedies which may have	Should not be given concomitantly unless agreed		
immune-modulating effects	by the sponsor		

11. Study procedures

11.1 Schedule of study procedures

Before study entry, throughout the study, and following study drug discontinuation, various clinical and diagnostic laboratory evaluations are outlined. The purpose of obtaining these detailed measurements is to ensure adequate safety and tolerability assessments. Clinical evaluations and laboratory studies may be repeated more frequently if clinically indicated.

11.1.1 For both treatment arms

- An early response evaluation will be performed 3-4 weeks after the first chemo-immunotherapy course
 (at the time of TRT start in the experimental arm). For patients randomized to the experimental arm,
 the CT planning scan might be used for response evaluation. For patients on the control arm, a regular
 CT scan must be performed.
- Response evaluation and measurement of HRQoL after completion of chemo-immunotherapy will be

performed 2-3 weeks after the fourth course

- If chemotherapy is discontinued before the fourth course, response evaluation and HRQoL measurement will be performed according to schedule (week 11-12).
- Subsequent tumor efficacy (RECIST) and other assessment dates are not affected by dose delays and remain as originally scheduled, as they are based on the date of inclusion and not the date of therapy.

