- Four courses of durvalumab 1500 mg IV day 1, carboplatin (AUC=5, Calvert's formula) IV day 1 and etoposide 100 mg/m² BSA IV day 1. On days 2-4, etoposide is administered in a dose of 100 mg/m² BSA IV or 200 mg/m² BSA PO. Chemoimmunotherapy courses are administered every three weeks. After completing four courses, durvalumab 1500 mg IV is given every four weeks until intolerable toxicity, patient's wish, or disease progression and need for other treatment.
- The dose of durvalumab will be adjusted to 20 mg/kg if a patient's body weight falls below 30 kg
- Patients randomized to the experimental arm will receive TRT of 30 Gy in 10 fractions, one fraction per day, 5 fractions per week, between the second and third chemo-immunotherapy course.
- Patients who achieve a response when evaluated after completion of chemo-immunotherapy may be offered PCI of 25 Gy in 10 fractions or 30 Gy in 15 fractions, one fraction per day, 5 fractions per week according to local treatment policy.

Safety assessments:

Toxicity will be classified according to CTCAE v5.0. Cognitive function will be assessed using the MoCA test. Patients will report HRQoL on the EORTC QLQ C30+LC13.

Efficacy assessments:

OS will be measured from the day of randomization until death by any cause, PFS from the day of randomization until RECIST 1.1 progression or death by any cause. Response to treatment and progression will be assessed according to RECIST 1.1. Response to treatment and progression will be assessed on CT and MRI scans at regular intervals. Sensitivity analyses including measurement of previously irradiated lesions (both thoracic lesions and brain metastases) will be performed.

Statistical methods and data analysis:

Cox proportional hazard method will be used to compare survival. The primary survival analyses will be performed 14 months after the last patient entry (to ensure that 1-year survival data are captured). Pearson's Chi-Square test will be used to compare toxicity, overall response rates, and treatment completion rates. Mann-Whitney's test will be used to compare number of completed chemo-immunotherapy- and durvalumab-courses.

Median OS will be estimated using the Kaplan-Meier method, and a Cox-model will be used for multivariable survival analysis adjusting for established prognostic factors in the target population (sex, PS, disease stage, presence brain metastases and liver metastases) and age. A separate analysis plan will be defined for the biomarker analyses.

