^hFor women of childbearing potential only. A urine or serum pregnancy test is acceptable. Women of childbearing potential are required to have a pregnancy test within 7 days prior to the first dose of study drugs and then before every durvalumab course. Pregnancy test may occur on Day 1, but results must be available and reviewed by the treating physician or Investigator prior to commencing an infusion.

Hepatitis B surface antigene (HBsAg), Hepatitis B core antibody (HBcAb), and Hepatitis C antibody (HCV Ab) tests are mandatory. If a patient has a negative HBsAg test and a positive HBcAb test, an HBV DNA test must be performed to determine if the patient has an HBV infection. If a patient has a positive HCV Ab test, an HCV RNA test must be performed to determine if the patient has an HCV infection.

FEV1, FEV1%, FVC, FVC%, and DLCO%

kRECIST assessments will be performed on images from CT of the chest and upper abdomen and MRI of the brain, each preferably with IV contrast. Additional anatomy should be imaged based on signs and symptoms of individual patients at baseline and follow-up. Confirmation of response is not mandatory. If an unscheduled assessment was performed and the patient has not progressed, every attempt should be made to perform the subsequent assessments at their next scheduled visit.

CT scan for radiotherapy planning may be used for patients in the experimental arm. A regular CT scan should be performed for patients in the control arm at the same time as CT scans for radiotherapy planning would be performed, usually 3-4 weeks after the first day of the first chemo-immunotherapy course.

^mMay be replaced with CT if MRI is unavailable.

ⁿArchival diagnostic material or re-biopsy for confirmation of suspected relapse.

^oNot mandatory.

Year	1				2					
Week	21	29	37	45	1	9	17	25	33	41
Durvalumab	D	urvalumab every	4 weeks until pr	ogressive diseas	e and need for o	ther treatment,	unacceptable to	kicity or patients	wish to disconti	nue
Clinical examination/ performance status/weight	х	х	х	х	Х	х	х	Х	Х	х
Concomitant medication	Х	Х	Х	Х	Х	X	X	Х	X	Х
HRQoL (QLQ C30 + LC13)	Х	X	X	Х	X		X		X	
Cognitive function (MoCA)	Х				Х					Х
Clinical chemistry ^e	Х	Х	Х	Х	Х	Х	Х	Х	Х	Х
Hematology	Х	Х	Х	Х	Х	X	X	Х	Х	Х
Pregnancy test in women of childbearing potential ^h					Before every du	urvalumab course	2			
Assessment of adverse events	Х	Х	Х	Х	Х	X	X	Х	X	Х
CT thorax/upper abdomenk	Х	Х	Х	Х	Х	Х	Х	Х	Х	Х
MRI of the brain ^{k,m}	(X)°	Х	(X)°	Х	(X)°	Х	(X)°	Х	(X)°	Х

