8.3.3 Treatment planning CT-scan

The treatment planning CT scan (or PET CT scan if that is the local routine) should be done with the patient immobilized in supine position according to local standard procedures for radiotherapy of the thorax. The whole thorax should be included in the CT scan and IV contrast should be used. Slice thickness should be \leq 3 mm. The use of 4DCT is recommended and breath-hold technique or gating is allowed, but not mandatory.

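### At week 3-4 only the TRT arm may be assessed on a planning CT that need not reach the upper abdomen, so extrathoracic response and progression can be recorded differently by arm

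*Protocol*

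**What the plan says.** The schedule in Protocol section 2 has a response evaluation at week 3-4, with a CT of thorax and upper abdomen marked for it. Footnote k places RECIST assessments on CT of the chest and upper abdomen plus brain MRI (no brain MRI is scheduled at week 3-4 in either arm). The same footnote adds: "Confirmation of response is not mandatory".

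Footnote l, attached to the week 3-4 CT, then separates the arms. For TRT patients: "CT scan for radiotherapy planning may be used for patients in the experimental arm". For controls: "A regular CT scan should be performed for patients in the control arm at the same time". Section 11.1.1 repeats this. It opens with "An early response evaluation will be performed 3-4 weeks after the first chemo-immunotherapy course", allows the planning scan in the experimental arm ("the CT planning scan might be used for response evaluation"), and makes a regular CT obligatory for controls.

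Section 8.3.3 describes the planning scan: "The whole thorax should be included in the CT scan and IV contrast should be used", with slices of 3 mm or less. A PET CT is also possible ("or PET CT scan if that is the local routine"). The upper abdomen is neither required nor excluded, and nothing asks for a supplementary abdominal scan when the planning CT replaces the regular one.

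The synopsis defines "PFS from the day of randomization until RECIST 1.1 progression or death by any cause". Section 14.1 lists overall response, response in non-irradiated lesions, PFS and PFS in non-irradiated lesions as secondary endpoints. The primary endpoint is 1-year overall survival.

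**The concern.** What is imaged at the first on-treatment evaluation may depend on the randomised arm. A control patient with liver or adrenal disease has it measured at week 3-4. A TRT patient with the same disease may not, if the planning scan ends at the thorax.

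The endpoints most exposed are those in non-irradiated lesions. Section 8.3.5 asks that all thoracic lesions be in the radiotherapy field where possible, so the lesions left unirradiated in the TRT arm will lie largely outside the thorax, where a thorax-only scan does not look. Section 5.1.1 uses response in non-irradiated lesions to look for synergy between radiotherapy and durvalumab, so an arm-dependent imaging rule there bears on a stated scientific aim.

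Two distortions are possible, in opposite directions. Because response needs no confirmation, an early extrathoracic response could be credited in controls and not seen in the TRT arm. Conversely, early progression confined to the abdomen could be dated at week 3-4 in controls and only at the next scan in the TRT arm.

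**Working it through.** The Protocol gives no figure on this point, so there is none to reproduce. The check sets the passages side by side and then illustrates size.

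**Coverage at week 3-4**

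| | TRT arm | Control arm |
|---|---|---|
| Schedule and footnote k | chest and upper abdomen | chest and upper abdomen |
| Footnote l, section 11.1.1 | planning CT may be used | regular CT required |
| Section 8.3.3 minimum for the planning CT | whole thorax | not applicable |

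Footnote k and footnote l agree only if the planning CT happens to extend to the upper abdomen. From week 11-12 onward the scan schedule is the same in both arms.

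**Delay in dating progression.** From week 3-4 to week 11-12 is 11 − 4 = 7 to 12 − 3 = 9 weeks.

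**Response, assumed inputs only.** Suppose:
- 5-15% of patients are not evaluable as responders at week 11-12;
- 30-60% of those had responded by week 3-4;
- 60% of those have abdominal target lesions;
- every TRT patient uses a planning CT that misses the abdomen;
- week 3-4 counts toward response.

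The excess in controls is then:
- low: 0.05 × 0.30 × 0.60 = 0.009, about 1 point;
- high: 0.15 × 0.60 × 0.60 = 0.054, about 5 points.

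None of these proportions is in the Protocol. Lower uptake or wider coverage shrinks the result in proportion.

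**Effect on the response test.** Take 151 per arm (302/2) and 65% response in both arms (section 4.1.2 gives approximately 65% for ES SCLC). The standard error of the difference is √(2 × 0.65 × 0.35 / 151) = 0.055. With a two-sided 5% test and a spurious excess d in controls, the rejection probability favouring control is P(Z > 1.96 − d/SE), and that favouring TRT is P(Z < −1.96 − d/SE):

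| d | d/SE | favouring control | favouring TRT | total |
|---|---|---|---|---|
| 3 points | 0.55 | 7.9% | 0.6% | 8.5% |
| 5 points | 0.91 | 14.7% | 0.2% | 15% |

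Almost all the excess rejection favours control. The chance of falsely claiming a TRT benefit on response falls from 2.5% to below 1%.

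**PFS.** A simulation with no true effect used 151 per arm and median PFS 5.2 months (the atezolizumab-arm figure in section 4.2.4) running from week 3.5. An assumed fraction of patients had upper-abdomen-only progression at week 3-4, dated at week 3.5 in controls and week 11.5 in the TRT arm:

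| Assumed fraction | Mean hazard ratio |
|---|---|
| 2% | 1.00 |
| 5% | 0.99 |
| 10% | 0.98 |

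There were 300 runs per setting. With up to 302 events per trial, the standard error of one log hazard ratio is roughly 2/√302 = 0.115, so the simulation error of the mean is about 0.115/√300 = 0.007. The 2% result cannot be told from no bias. A separate run of 3,000 simulated trials, with 2-8% assumed, gave 0.995 to 0.988. The direction favours TRT and the size is small.

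**The case against.** The strongest reply is that the text permits a difference without creating one. The planning scan is optional, the thorax is a minimum coverage, PET CT is allowed, the schedule names the upper abdomen for both arms, and footnote k asks for further anatomy to be imaged as signs and symptoms suggest. All of that stands. A reader might infer that TRT patients will be assessed on thorax-only scans, but the Protocol does not say so.

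Second, no section says that the week 3-4 evaluation counts toward overall response. Section 11.1.1 lists it apart from the evaluation after chemo-immunotherapy, and the absence of a confirmation requirement does not settle which scans count. That rule may properly sit in a statistical analysis plan. This also stands, so the response part of the point is conditional. It does not remove the point, because the imaging rule by arm is fixed in the Protocol and no later plan can recover abdominal images that were not acquired.

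Third, section 5.1.1 already compares non-irradiated lesions in the TRT arm with overall response in controls, so different lesion sets are compared at every scan. That is true and is a separate asymmetry. The week 3-4 rule adds to it and does not explain it.

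**Conclusion.** The point holds as an unreconciled pair of rules. RECIST coverage is set at chest and upper abdomen, yet one arm alone may substitute a scan required to cover only the thorax. Where that happens, extrathoracic findings at week 3-4 can be recorded only in controls.

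If week 3-4 counts toward response, the bias favours control on overall response and on response in non-irradiated lesions. Its size is unknown. The 1 to 5 points depend entirely on assumed proportions and full uptake of thorax-only scans. On PFS the bias favours TRT and is very small, with a hazard ratio of about 0.98 to 1.00 when 2-10% of patients are assumed to have abdomen-only progression at that time.

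Two stronger readings are tempting and unsupported. One is that the 8.5% and 15% rejection rates mean more false claims for TRT. They are nearly all rejections in favour of control, so for a hypothesis that TRT improves response the bias is conservative, and it could mask a real benefit. The other is that the trial's main conclusion is at risk. Primary 1-year overall survival does not depend on imaging and is unaffected. This is a minor point, worth correcting because the correction is cheap.

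**What to change.** Reconcile footnotes k and l of the schedule with sections 8.3.3 and 11.1.1 so that one rule applies to both arms. Either option removes the asymmetry in response:

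1. The week 3-4 CT used for RECIST covers chest and upper abdomen in both arms. The planning CT may serve if it is extended that far. The cost is slightly longer planning-scan coverage in the TRT arm.
2. The whole week 3-4 time point is excluded from overall response and from response in non-irradiated lesions in both arms, and week 11-12 is the first response evaluation. The cost is losing early responses that are no longer present or evaluable at week 11-12.

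Do not score thoracic findings and discard abdominal ones from the same scan. That is not a RECIST overall assessment.

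For PFS, keep RECIST 1.1 progression as observed in the main analysis, in line with the synopsis definition and section 12. Add a sensitivity analysis that dates extrathoracic-only progression seen at week 3-4 to the next scan common to both arms. This needs one derivation rule and no further data.

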11.1.2 For durvalumab maintenance therapy

- Patients may delay dosing under certain circumstances such as e.g. intercurrent disease and holidays if this is considered appropriate by their physician.
- Dosing may be delayed per Toxicity Management Guidelines, due to either an immune or a non-immune-related AE.
- If dosing must be delayed for reasons other than treatment-related toxicity, dosing will resume as soon as feasible
- Dosing intervals of subsequent cycles may be shortened as clinically feasible in order to gradually align treatment cycles with the schedule of tumor efficacy (RECIST) and patient reported outcomes (PRO) assessments. Subsequent time between 2 consecutive doses cannot be less than 22 days, based on the half-lives of durvalumab (see current Investigator Brochure for durvalumab).

